1. Confirmed COVID-19 positive test result (including presumptive positive).
2. Hospitalization
3. Requiring ≥ 4 liters/min O_2 nasal cannula to maintain oxygen saturation $\geq 92\%$, but not mechanically ventilated
4. Age ≥ 18 years old.
5. Access to a phone in the hospital room or an electronic device that is capable of receiving phone calls and/or video calls and/or e-mail.
6. Able to read/write/speak English or Spanish fluently.
7. Subjects must have the capacity to provide consent or an appropriate Legally Authorized Representative (LAR) to provide informed consent.
8. Negative pregnancy test for women of childbearing potential.

Exclusion Criteria:

1. Severe allergy to any IVIG product formulation
2. History of DVT, PE, thromboembolic stroke or other thrombotic events

3. Hypersensitivity to corn. Octagam® contains maltose which is a sugar derived from corn.
4. Uncontrolled hypertension (SBP>180 mm Hg or DBP>120mmHg)
5. Active participant in another research treatment study
6. Mechanically ventilated patient
7. Code status is Do Not Resuscitate or Do Not Intubate

Age of Subjects: ≥18 years of age

Gender of Subjects: Either male or female

Racial and Ethnic Origin: Non-specific

Vulnerable Subjects: Hospitalized subjects

Study Design: Investigator initiated, open label, multicenter, two arm, randomized study to compare the impact of adding IVIG to the Standard of Care (SOC) to the SOC without IVIG. Randomization ratio will be 1:1.

Procedures and Study Visits:

1. The PI will be notified of a COVID-19 tested positive patient via hospital generated alert.
2. The PI or designee will prescreen the patient using the inclusion and exclusion criteria.
3. PI or Sub-I will contact the study team, if the patient passes prescreening.
4. The CRC will obtain an informed consent from the subject or LAR either electronically utilizing DocuSign® or with a paper copy utilizing an impartial witness:
 - a. The research team will utilize DocuSign® for the signing of the consents in order to be compliant with the infection control measures taken place for Highly Infectious Diseases. Below are the steps of the DocuSign® procedure:
 - i. Upon receiving confirmation of the subject passing prescreening, the CRC will call the subject/LAR to assure the consent process is being conducted in a private place and manner and obtain a valid email address. If the subject does not have a valid email address, instructions will be provided to help them set up an email address account. The CRC will also ask the subject/LAR if he or she would prefer to have the consenting process conducted via video call if this technology is available to all persons involved in the consent discussion).
 - ii. If the subject/LAR agrees to participate the CRC will send the DocuSign® instructions via email to the subject.
 - iii. The CRC will send out Consent via DocuSign® to the subject/LAR (it will appear in their email inbox).
 - iv. Subject/LAR will use any electronic device that is able to access DocuSign® email and open consent. Subjects/LAR may be instructed to

- place their phone on speaker mode (while maintaining privacy) to ensure that they can see the consent during the process.
- v. The CRC will consent subjects/LAR via phone. CRC will ask the subject/LAR to verbally confirm that he or she is alone in the room to ensure privacy and confidentiality. If the subject/LAR wishes to include additional participants (e.g., next of kin) in the informed consent discussion, the subject/LAR may add the additional participant(s) to the call.
 - vi. Subject/LAR will sign consent using any electronic device that is compatible with DocuSign®. Once they are finished, the consent will be sent to the CRC's email inbox and the CRC will sign the consent electronically.
 - vii. Subject/LAR will have a digital copy of the signed consent accessible through DocuSign®. The subject/LAR may also request a printed copy of the signed consent to be mailed to their home address.
 - viii. After the consenting process, the CRC will download an electronic copy of the consent from DocuSign®. The CRC will email the subject/LAR an electronic copy of the consent and print out a copy for the site's research binder. After this, the CRC will delete the stored copy in DocuSign®. The CRC will also delete the subject contact information stored in DocuSign®.
- b. If the subject/LAR is unable or unwilling to use DocuSign®, the informed consent process may be conducted via phone, or via video conference (if this technology is available to all persons involved in the consent discussion). An impartial witness will be present during the consenting process.
- i. Upon receiving confirmation of the subject passing prescreening, a nurse or investigator will provide a paper copy of the consent to the subject/LAR when they enter the room for the provision of routine care. The CRC will call the subject to assure the consent process is being conducted in a private place and manner. The CRC will also ask the subject/LAR if he or she would prefer to have the consenting process conducted via video conference. An impartial witness will be added to the phone or video call. If the subject/LAR wishes to include additional participants (e.g., next of kin) in the informed consent discussion, the subject/LAR may add the additional participant(s) to the call.
 1. The CRC will review the informed consent with the subject/LAR and respond to any questions the subject may have.
 2. The impartial witness will confirm that the subject's/LAR's questions have been answered.
 3. The CRC will confirm that the subject/LAR is willing to participate in the trial and sign the informed consent document while the witness is listening on the phone.

4. The subject/LAR will verbally confirm that they would like to participate in the trial and that they have signed and dated the informed consent document that is in their possession.
 - ii. If feasible, the subject/LAR or hospital staff will take a picture of the informed consent document signature pages to be saved with the study records. If this is not feasible, a signed and dated attestation will be obtained from the impartial witness who participated in the call and from the person obtaining informed consent, confirming that the subject/LAR agreed to participate in the study and that they signed the informed consent. The CRC will save the signed/dated attestation with the study record.
5. A urine or blood pregnancy test will be ordered using urine or blood previously collected for routine care for subjects of childbearing potential who have passed all the other screening criteria and signed consent. If no leftover urine or blood is available, the patient will be asked to take a urine pregnancy test. If the patient already had a pregnancy test during their hospitalization, the results will be extracted from the EMR and used to determine eligibility.
6. The designated research team member will randomize the subject. The randomization will be computer generated using this website in a block of 10. (<https://www.sealedenvelope.com/simple-randomiser/v1/lists>).
7. If the subject is randomized to the “study arm”, then the Research Pharmacy will enter in the order for the IVIG and will not charge the subject. If the subject is randomized to the SOC arm, there is no additional work to be completed by the Research Pharmacy.
8. There are 3 endpoints for this study: discharge to home, receipt of mechanical ventilation, or death. Once one of these endpoints is reached, the subject’s participation in the study will end. As such, the subject may be a candidate for enrollment in another research protocol where appropriate.

Dose: IVIG (Octagam) 0.5g/kg IVPB actual body weight daily x 3 days, with premedication methylprednisolone 40 mg IV push x 1 30-50 minutes before each IVIG infusion.

- Initial infusion rate of IVIG (Octagam) will be of **0.6 mL/kg/hour**, increasing to a maximum rate of 100ml/hr, if tolerated. This is consistent with the standard of care for IVIG at Sharp HealthCare.

Procedure Classification: Aside from a urine or blood pregnancy test for subjects of childbearing potential, there are no other extra tests, imaging scans or procedures that will be performed as part of the study.

Potential Hazards and Precautions: Potential hazards to subjects are described in the “Potential Risks” section, and precautions for subjects are described in the “Protection Against Risks” section.

Research team members will take precautions to minimize exposure to COVID-19 infection by obtaining informed consent electronically, and by collecting data from routine clinical tests as opposed to conducting protocol-specific tests.

Study Timeframe: The study time frame would be from IRB approval date to the end of the pandemic or until our sites reach 40 subjects, whatever comes first. We anticipate that at the current COVID-19 rate, it should take about 6 weeks to enroll all patients from the time of study initiation.

The end of study for each individual subject will be the date of discharge from the Sharp HealthCare hospital. The subject will not be followed if there is a transfer to a non-Sharp hospital or any sub-acute care setting (i.e., SNF, LTAC, rehabilitation center). A subject's participation will also end if the subject's goals of care have transitioned to palliation, including changing the code status to Do Not Resuscitate or Do Not Intubate of which would render the patient no longer a candidate for intubation.

Method of Subject Identification and Recruitment: The PI or Sub-I will be notified of a COVID-19 confirmed positive patient via hospital generated alert as part of the Infectious Disease Team at each hospital.

Subject Capacity: Subjects who are cognitively impaired or lack the capacity to provide informed consent (as described in HRP-013 section 5.2) may be enrolled in the study if they have an appropriate LAR to provide written informed consent on their behalf. The researchers will follow the guidance outlined in HRP-013 "Legally Authorized Representatives (Surrogate Consent)" when obtaining surrogate consent.

Subject/Representative Comprehension: Subjects/LARs must have the ability to understand the requirements of the study, provide informed consent, and provide authorization of use and disclosure of personal health information. Subjects with impaired cognitive or decision-making capacity (determined by the PI or designee's assessment of the subject's ability to understand and express a reasoned choice, according to HRP-013 section 5.2.1) must have an appropriate LAR to provide consent on their behalf. If the research subject lacks capacity to consent, the investigator will describe the research to the subject in a manner consistent with the standard consent process and indicate the intent to obtain surrogate consent. This communication will be documented in the research record. If the research subject is non-responsive, the investigator will document this observation in the research record and a note in the subject's medical record that references the research record. If the research subject expresses resistance or dissent to being in the research or to the use of the surrogate consent by word or gesture, she/he will be excluded from the research study.

Documentation of Consent/Assent: Consenting will be conducted as described above in the Procedures and Study Visits section. Consents will be printed and stored in the subject's research binder in a secure location.

Reimbursements or Payments: None

Costs to the Subject: None

Data Sources: Sharp HealthCare electronic medical records (EMR) for hospital in-patients who meet inclusion criteria at acute care facilities.

Data Collection/ Assessment Instruments: The Case Report Form will include the following data elements: Demographics (age, gender, race/ethnicity, insurance), medical status (pre-existing comorbid conditions (based on the Charlson Comorbidity Index), ferritin level (results will only be collected if lab is ordered as part of the subject's standard of care), CRP level. The tool used to calculate the Charlson Comorbidity Index can be found here <https://www.mdcalc.com/charlson-comorbidity-index-cci#next-steps>). Other data to be collected from standard of care procedures includes vital signs, result of blood or urine pregnancy test, serum creatinine, calculated creatinine clearance (Cockcroft and Gault equation), white blood cell count, platelet count, maximum body temperature in the past 24 hours and oxygen demand rate, whether or not there is an admission to the ICU, any concomitant antimicrobials including azithromycin, doxycycline, hydroxychloroquine, chloroquine, and remdesivir. Receipt of interventions will include standard of care in those who have tested positive for COVID-19. Measures of healthcare service utilization will include length of stay, number of days in ICU, number of days requiring oxygenation, discharge disposition and mortality.

Data Collection Resources: The Study Coordinator will complete the Case Report Forms, with assistance from Sharp's Clinical Analytics team to extract information from the EMR.

Data Analysis: Descriptive statistics will be conducted to describe frequencies of demographics and clinical characteristics including the following: age at discharge, gender, race/ethnicity, payer, comorbid conditions based on the Charlson Comorbidity Index, receipt of medical interventions (mechanical ventilation, medications) and healthcare service utilization (ICU admission and Length of Stay in the hospital). Frequencies and descriptive statistics will be conducted using chi-square or 2-tailed Fisher exact statistics depending on the final sample size for categorical data and t-tests for continuous data. Kaplan-Meier analysis will be performed with assistance from a biostatistician regarding the endpoints of mechanical ventilation and discharge to home endpoints. We do not anticipate number of patient deaths for be sufficient for a meaningful analysis.

Privacy of Subjects: There will be limited access to the subject due to standard of care isolation protocols. The Informed Consent process will emphasize the personal nature and privacy

concerns related to communications regarding the subject's condition and infectious disease test results.

Confidentiality of Data and Storage: Subjects information will be recorded on a master list accessible to the investigator and research staff. It will be stored electronically on a secure server. Information included on master list: subject ID, hospital, date screened, patient name/room#, FIN, group, age, gender, enrollment status, telephone number, email address, and address. All binders will be stored and secured at Sharp's Center for Research office in accordance with all regulatory and organizational requirements, and will be accessed only by authorized personnel. No subject-specific data will be reported. Sharp FIN will be used to link subject records across data systems and hospital visits. Protected Health Information (PHI) will be safeguarded as specified by Sharp HealthCare policy. There is a risk of disclosure of PHI from inappropriate access to the study database. All efforts will be made to protect PHI, including password protecting the database with access only allowed to study members who are Sharp HealthCare employees. All datasets will be de-identified prior to any statistical analyses conducted by the Statistician. Identifiers will be destroyed two years after study end date, once data has been aggregated for reporting.

Data Monitoring: A designated person (or group of designees) who is not part of the Research Team will review and will report the outcomes to the SHC IRB after a total of 10, 20, and 40 patients (5, 10, and 20 in each arm, respectively) have completed/met the endpoint of the study. Additionally, if unexpected adverse outcomes are identified at any point in the enrollment the designated person will review the case on an individual basis.

Benefits to Individual Subjects: Potential reduction in ICU hospitalization, potential avoidance of mechanical ventilation and potential decrease in length of stay in the hospital.

Potential Benefits (Value) to Society: Any data collected will be a benefit to society whether we prove or disprove the hypothesis. However, if it is determined that the studied intervention indeed does reduce demand for mechanical ventilation and ICU care, it may provide significant relief to a medical care system that is anticipated to be overwhelmed at pandemic peak. The benefits will most likely be realized in the next SARS-CoV-2 epidemic. There are potential benefits to each institution that participates in this study to reduce the demand of mechanical ventilation and reduce the demand for isolated negative pressure ICU rooms.

Risk Category: Greater than minimal risk

Potential Risks: All of the adverse reaction and hypersensitivities are detailed in the package insert. These risks are also explained in layman's terms in the Informed Consent Form. The most common adverse reactions include the following: Headaches, allergic reaction and anaphylaxis, aseptic meningitis, venous thrombosis.

Protection Against Risks:

1. Pre-medicate with methylprednisolone IV to reduce/avoid infusion related reactions, including headache, aseptic meningitis.
2. The subject will be in the in-patient acute care setting with the Standard of Care monitoring as would be done if the drug were to be administered outside of the study setting.
3. If the subject experiences side effects that are suspected to be due to the IVIG for subjects in the study group, it will be up to the discretion of the treating clinician/PI whether to continue the IVIG or not.
4. There are no adequate and well-controlled studies of methylprednisolone in pregnant women, and it is not known whether Octagam 10% can cause fetal harm when administered to a pregnant woman or can affect reproduction capacity. Therefore, pregnant women are excluded from participation, and women of childbearing potential will undergo a blood or urine pregnancy test prior to randomization.

Termination of the Study:

1. If the subject prematurely stops study treatment, the study team will continue to collect data until discharge.
2. If the subject progresses into mechanical ventilation, those who are actively receiving IVIG will be stopped.
3. If there are additional doses schedule per protocol and the subject has progressed into the intensive care unit, the additional doses will not be administered.
4. The patient retain the right to terminate the study drug for any reason.
5. Discharge to home

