COVID-IVIG Protocol Cover Page

Study Title: Randomized Open Label Study of Standard of Care Plus Intravenous Immunoglobulin(IVIG) Compared to Standard of Care Alone in the Treatment of COVID-19 Infection

NCT Number: NCT04411667

Document Date: 19May2020

Protocol name: COVID-IVIG

Principal Investigator: [name]; [contact]; [contact]
IRB # 2004902

Title: Randomized Open Label Study of Standard of Care Plus Intravenous Immunoglobulin (IVIG) Compared to Standard of Care Alone in the Treatment of COVID-19 Infection

Primary Objective:

1. To identify whether or not IVIG can halt the progression to respiratory failure requiring mechanical ventilation in subjects admitted to the hospital with confirmed COVID-19.

Secondary Objectives:

1. To identify whether adding IVIG to the standard of care will reduce days requiring oxygen therapy.
2. To identify whether adding IVIG to the standard of care will reduce total hospital days.

Hypothesis: We hypothesize that the addition of IVIG will be beneficial in abating acute lung injury in subjects with SARSCoV-2 induced hypoxia that results in organ injury in such patients.

Background: Coronaviruses has been known zoonotic pathogens since the early 1970's. Bats have been identified as the main natural reservoir and domesticated animal intermediary species (e.g., camels, cats) have facilitated transmission to humans. In late 2019, a novel coronavirus (SARS-CoV-2) emerged in humans, originating in Wuhan, China and spreading across the globe as a pandemic, causing coronavirus disease of 2019 (COVID-19).

The current mortality rate (17MAR2020) is not well described because of the shortage of laboratory testing assays worldwide. Using WHO data on the cumulative number of deaths to March 1, 2020, mortality rates would be 5.6% (95% CI 5.4–5.8) for China and 15.2% (12.5–17.9) outside of China⁸.

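### Oxygen days cannot show recovery in home-oxygen users: inclusion 3 accepts a need that is not new, and home oxygen flow is not a listed data item

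*Combined protocol and SAP*

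**What the plan says.** Inclusion Criteria item 3 sets a threshold on current flow: "Requiring ≥ 4 liters/min O_2 nasal cannula to maintain oxygen saturation" of at least 92%, in a patient who is not mechanically ventilated. It does not require the need to be new, caused by COVID-19, or above what the patient used before admission. The seven exclusions, of which the last is "Code status is Do Not Resuscitate or Do Not Intubate", do not mention chronic or home oxygen.

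The Hypothesis is narrower. It concerns "subjects with SARSCoV-2 induced hypoxia".

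Secondary Objectives item 1 is "To identify whether adding IVIG to the standard of care will reduce days requiring oxygen therapy". Under Data Collection/Assessment Instruments, the measure appears among the service-utilization items as "number of days requiring oxygenation, discharge disposition and mortality". The clinical items listed there include "maximum body temperature in the past 24 hours and oxygen demand rate" and comorbid conditions based on the Charlson index, but not oxygen use before admission.

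On follow-up, Study Timeframe states: "The end of study for each individual subject will be the date of discharge from the Sharp HealthCare hospital". Participation also ends at mechanical ventilation, death, a move to palliation, or transfer to a hospital outside the system or to sub-acute care. Data Analysis plans t-tests for continuous data, and Kaplan-Meier analysis for ventilation and discharge home only.

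**The concern.** Oxygen days are meant to show whether IVIG speeds recovery from acute hypoxia. That works only if a recovered patient stops accumulating days. A patient on continuous oxygen at home never reaches a day without oxygen, so under a plain count every day in study is an oxygen day, however well the acute illness has resolved. The entry rule lets such patients in, and the listed data give the analyst no home flow to subtract. For them the first secondary outcome becomes a copy of time in study, which is close to the second secondary outcome, total hospital days. With 20 patients per arm, even a few such values weaken the contrast and add noise.

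**Working it through.** **Inputs from the documents.** Total sample 40 (Study Timeframe); allocation 1:1 (Study Design), so 40/2 = 20 per arm, which agrees with Data Monitoring; t-tests for continuous data (Data Analysis). The documents give no power, effect size, standard deviation or share of home-oxygen users, so there is no planned figure to reproduce.

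**Step 1: what the count measures.** Let T be a patient's days in study and R the days on which the flow needed exceeds the flow used at home. For a patient with no home oxygen, any day on oxygen is a day above home flow, so the plan's count equals R. For a continuous home-oxygen user the plan's count equals T, whatever R is. The T − R days after return to the usual flow are scored the same as days of acute need. This also affects a patient on 3 L/min at home who has a real rise to 4 L/min: after full recovery to 3 L/min, each further day still counts.

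**Step 2: can the listed data separate T from R?** No. Oxygen demand during the admission is recorded, but the home level is not, and a comorbidity index does not supply a flow.

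**Step 3: illustrative size.** Assume that a share f of patients shows no effect on oxygen days, that the standard deviation is unchanged, and that the test is two-sided at 0.05.

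Standardized difference detectable with 80% power at f = 0:
δ = (1.960 + 0.842) × √(2/20) = 2.802 × 0.316 = 0.886.

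Diluted power = Φ(δ(1 − f)/√(2/20) − 1.960) = Φ(2.802(1 − f) − 1.960).

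Chance that at least one such patient enrols = 1 − (1 − f)^40.

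| Assumed f | Expected patients of 40 | Chance of at least one | Power |
|---|---|---|---|
| 0% | 0 | 0% | 80.0% |
| 1% | 0.4 | 33.1% | 79.2% |
| 2% | 0.8 | 55.4% | 78.4% |
| 5% | 2 | 87.1% | 75.9% |
| 10% | 4 | 98.5% | 71.3% |

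**Step 4: chance imbalance.** If 2 such patients enrol, the chance that both fall in the same arm is 2 × C(20,2)/C(40,2) = 380/780 = 0.487. If 4 enrol, the chance that the arms differ by 2 or more is 1 − C(20,2)²/C(40,4) = 1 − 36,100/91,390 = 0.605. Uneven splits are therefore common, but either direction is equally likely.

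**The case against.** The strongest reply is that this is a small measurement matter. Home-oxygen users may be few, and at a share of 1% to 2% the illustrated power loss is under two percentage points. Randomization makes an uneven split equally likely in either direction, and the standard error of the t-test already allows for it. A pragmatic trial may also choose to include chronic oxygen users. All of this stands. It limits the size of the problem but does not give the count a meaning for these patients.

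A reader might infer more than the documents support:

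- *That these patients can never complete the outcome.* The plan defines no finishing event. It counts days, and the count closes when participation ends. The value is finite and recorded; it is just uninformative about recovery.
- *That they cannot show an effect on the primary outcome.* A home-oxygen user can still progress to ventilation, and ventilation and hospital days remain measurable. Someone whose usual flow is below 4 L/min meets item 3 only through a real increase. A lack of acute deterioration describes only those already at 4 L/min or more at home with no rise.
- *That they could never be identified afterwards.* The listed fields omit home oxygen, but the source is the electronic record, and Confidentiality of Data and Storage describes linkage across data systems and hospital visits. Later chart review is not ruled out. The point is that the planned data set would not allow it.
- *That the comparison is biased.* Nothing in the entry rule favours one arm.

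**Conclusion.** The concern holds as a gap in outcome definition and data collection. Item 3 admits a pre-existing oxygen need, home flow is not a listed item, and for a continuous home-oxygen user the planned count reduces to days in study. The consequence is dilution and chance noise in the first secondary outcome.

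Its size cannot be fixed from the documents. Across the assumed shares of 1% to 10%, power falls from 80% to about 79% to 71%. The 80% starting point is a reference, not a claim of the plan, and it already requires a difference of about 0.89 standard deviations. Treating the affected patients as showing no effect is also a simplification: if IVIG shortened their stay, their count would fall too, and the dilution would be smaller.

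There is also a mismatch between item 3 and the population named in the Hypothesis. Whether to close it by narrowing entry is a trade-off between a cleaner population and broader recruitment, and the documents do not settle it.

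**What to change.** 1. Add one baseline item to the case report form: home oxygen flow before this admission, entered as 0 if none.
2. Define an oxygen day as a day on which the flow needed exceeds that home level. For patients without home oxygen this leaves the count unchanged.

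The cost is one extra chart item, one sentence in the outcome definition, and reliance on the home flow as recorded. The 4 L/min and 92% thresholds are untouched.

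The rule repairs the count for home-oxygen users who had an acute rise. A patient who enters at the usual flow with no rise would score zero in either arm, which is accurate but still uninformative. The new field would at least allow an analysis without such patients. Requiring a need above the home flow in item 3 would keep them out, though it would still admit a patient who goes from 3 to 4 L/min. That choice should be made and stated by the investigators.

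### The protocol publishes one block size of 10 in an open-label trial and does not separate the list holder from recruitment, so staff who can see past assignments could anticipate some allocations

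*Combined protocol and SAP*

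**What the plan says.** Study Design describes an "Investigator initiated, open label, multicenter, two arm, randomized study" with 1:1 allocation. Under Procedures and Study Visits:

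- Item 2: "The PI or designee will prescreen the patient using the inclusion and exclusion criteria". Patients who pass are then referred to the study team (item 3).
- Item 4: "The CRC will obtain an informed consent from the subject or LAR".
- Item 5 places the pregnancy test among subjects "who have passed all the other screening criteria and signed consent", so consent and the other eligibility checks come before randomization.
- Item 6: "The designated research team member will randomize the subject. The randomization will be computer generated using this website in a block of 10". The website address given there suggests a list made in advance, but the text does not say so.
- Item 7 brings in the Research Pharmacy only after assignment, to enter the IVIG order: "If the subject is randomized to the SOC arm, there is no additional work to be completed by the Research Pharmacy".

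Study Timeframe continues enrolment "until our sites reach 40 subjects", unless the pandemic ends first, and expects that "it should take about 6 weeks to enroll all patients". Confidentiality of Data and Storage lists *group* among the items on a master list that the investigator and research staff can open. The term is not defined there.

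**The concern.** When treatment is open and the block size is known, anyone who sees past assignments can count how many of each arm remain in the current block. Towards the end of a block the next arm becomes likely, and then certain.

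Consent before randomization protects the last step only. The exposure comes earlier, when an alerted patient is prescreened and referred or the approach is timed. A person who expects a particular arm may influence those decisions, even without intent. The arms could then differ in prognosis before treatment starts, and the analyses described under Data Analysis include no adjusted comparison. The protocol states no safeguard at this step, such as independent custody of the list.

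**Working it through.** **Inputs.** From the protocol: block size 10, ratio 1:1 (so 5 and 5 per block), 40 subjects, open label, about 6 weeks of accrual. Assumed: the observer knows all past assignments on the list; one list, or a separate list in each of 2, 3, 4 or 6 hospitals. The protocol gives no predictability figure to reproduce.

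**Certain allocations, block of 10.** The next allocation is certain once one arm has used its 5 places. After k assignments (k = 5 to 9) the probability is 2 x C(5, k-5) / C(10, k).

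| Position in block | Formula | Certain with probability |
|---|---|---|
| 6th | 2 x 1/252 | 0.8% |
| 7th | 2 x 5/210 | 4.8% |
| 8th | 2 x 10/120 | 16.7% |
| 9th | 2 x 10/45 | 44.4% |
| 10th | 2 x 5/10 | 100% |

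The sum is 1.667 per block, which agrees with the closed form 2m/(m+1) = 10/6 for m = 5. Four blocks give 4 x 1.667 = 6.7 of 40.

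**Guessable allocations.** Always guessing the under-filled arm is right m + 2^(2m-1)/C(2m, m) - 1/2 times per block: 5 + 512/252 - 0.5 = 6.53 of 10, or 26.1 of 40 (65%). With no information it would be 20 of 40 (50%).

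**Separate hospital lists.** Block counting then works only in blocks that a hospital nearly fills.

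| Hospitals (assumed) | Certain of 40, equal split | Certain of 40, random accrual |
|---|---|---|
| 2 | 6.7 | 5.4 |
| 3 | 5.0 | 4.8 |
| 4 | 6.7 | 4.2 |
| 6 | 0.2 | 1.8 |

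The guess rate is 58-65% across these cases.

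**List itself visible.** All 40 allocations are known, whatever the block size.

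**Possible bias (illustration).** Take one list, with steering at every certain allocation. On average 3.33 of the 20 subjects in each arm are affected. Let *gap* be the assumed difference in risk between patients steered to standard of care and to IVIG, so that each arm shifts by half of it. Bias = 2 x (3.33/20) x (gap/2) = 0.167 x gap. Gaps of 10 and 20 points give 1.7 and 3.3 points. If only half of the certain allocations can be acted on, the bias is 0.8 and 1.7 points.

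The random SD of the risk difference with 20 per arm is sqrt(2p(1-p)/20). This is 12.6 points at an assumed risk p = 20% and 15.8 at p = 50%. The full-steering bias is therefore between 1.7/15.8 = 0.11 and 3.3/12.6 = 0.26 of one SD.

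**Opportunity.** 40 subjects in 42 days is 0.95 a day across all sites. The protocol does not say how often a recruiter would have a choice of patient.

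**Randomly varied blocks.** This was simulated with 20,000 lists of 40 and an observer who knows the possible sizes and all past assignments.

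| Block sizes | Certain of 40 | Guess rate |
|---|---|---|
| 10 only | 6.7 | 65% |
| 4/6/8 | 0.9 | 68% |
| 6/8/10 | 0.7 | 66% |

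**Cost in balance.** At 40 randomized, varied blocks leave the arms differing by 2 in 27-33% of lists and by 4 in about 0.3-1.2%. The SD of the risk difference rises by sqrt((1/19 + 1/21)/(2/20)) = 1.001, or 0.1%, for 19/21, and by sqrt((1/18 + 1/22)/(2/20)) = 1.005, or 0.5%, for 18/22.

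**The case against.** Much of this rests on silence. The protocol uses different role names for prescreening, consent and randomization, and nothing shows that one person does more than one of them. A reader might infer that the person who recruits also holds the list, or that allocation is unconcealed. The text supports neither: it does not merge these roles, and it does not separate them. Nor does it say that the block size is fixed; that is only the natural reading of a single stated size. *Group* meaning the arm is likewise an inference. One part of the protocol, between the background and the inclusion criteria, was not available to check. All of this stands, and it is why the point is conditional.

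The practical risk also looks modest. Patients are identified by hospital alert, most eligibility criteria are objective, and accrual of about one a day across sites may leave little choice of patient. A block of 10 is less predictable than smaller fixed blocks: with blocks of 4, a third of allocations are certain. This stands too, and it lowers the grade.

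Finally, no single remedy does everything. Independent custody protects the list itself but does not change the block-counting figures. Varied blocks remove most certainty but not the guessing. Restricting *group* helps little if coordinators work across hospitals, because treatment is open. These limits are correct. They argue for combining custody with varied blocks and for treating the restricted log as optional.

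**Conclusion.** The point holds as a minor, conditional one. As written, the rules would let staff who can see past assignments count the block before a patient is referred or approached. With one list, that makes about 6.7 of 40 allocations certain and about 65% guessable; with many separate hospital lists fewer are certain. If the list itself is open to recruiters, all 40 are known.

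A reader might go further and infer that selection bias will occur or that it threatens the result. The documents do not support that. Even with steering at every certain allocation, the illustrated bias of 1.7-3.3 points is small against a random SD of about 13-16 points, and it rests on assumed risk gaps of 10-20 points. That illustration covers block counting only, not open access to the list. The reason to act is that a standard safeguard costs almost nothing.

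**What to change.** Amend item 6 of Procedures and Study Visits in two ways.

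1. State that the list is generated and held by someone with no role in prescreening, referral or consent, and that each assignment is released only after consent and eligibility are complete. The Research Pharmacy is one option, as a new duty. This closes the case in which all allocations are known.
2. Replace the single block of 10 with randomly varied block sizes, recorded outside the protocol. This addresses certainty from block counting.

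Optionally, move *group* from the shared master list to a restricted log. This limits what is known only for staff who see a single hospital.

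The cost is a wording change, a new list and a small task for the list holder. An exact 20/20 split at 40 randomized, which one list in blocks of 10 now gives, would no longer be assured, with the negligible loss of precision shown above. The reviews planned at exactly 5 and 10 per arm are not assured now either, because they count subjects who have completed rather than those randomized. Because treatment is open, predictability is reduced, not eliminated.
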